#### **6.1.1 Dose Modifications, Interruptions and Delays**

Reduction/interruption of dosing for adverse events may take place at any time during the study.

Diarrhea and skin rash are the major side effects associated with erlotinib. Other known side effects include dry skin, fatigue, pruritus, nausea, vomiting, anorexia, abdominal pain, gastrointestinal perforation, dry mouth, dry eye, and headache. Dose reductions can be made according to the system exhibiting the greatest degree of toxicity. All toxicities will be graded according to the NCI CTC-AE version 4.0.

Upon the onset of an AE deemed by the investigator to be related to the study drug, treatment will be interrupted until AE resolution and then restarted at reduced dose of erlotinib. Once a patient has a dose reduction for toxicity, the dose will not be re-escalated except in the case of erlotinib related rash.

The dose of erlotinib will be decreased in 50 mg steps according to the schedule displayed in Table 1.

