**Table 1 Dose Level Reductions**

Starting Dose	First reduction	Second reduction
150 mg/day	100 mg/day	50 mg/day

The following guidelines in Table 2 outlines dose adjustments according to the most common toxic effects. In the event of a rash, dose can be re-escalated when rash is  $\leq$  grade 2. Should a patient experience more than one toxic effect, the dose should be reduced.

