**Table 2 Guidelines for management of erlotinib-related toxic effects:**

Toxicity	Grade	Guideline for management	Dose modification of erlotinib*
Keratitis	2	Interrupt the treatment. Ophthalmologic assessment.	Hold until recovery, and then restart at reduced dose. Continue regular ophthalmological assessments while

			on treatment.
	$\geq 3$	Discontinue treatment and seek ophthalmological advice	
Diarrhea	1	No intervention	None
	2	Loperamide (4 mg at first onset, followed by 2 mg every 2-4 hours until diarrhea-free for 12 hours)	None**
	3		Hold until recovery to $\leq$ grade 1, and then restart at reduced dose.
	4	Discontinue treatment	
Rash	1	No intervention	None
	2	Any of the following: minocycline a , topical tetracycline or clindamycin, topical silver sulfadiazine, diphenhydramine, oral prednisone (short course)	None**
	3		Hold until recovery to $\leq$ grade 2, and then restart the dose.
	4	Discontinue treatment	
Other toxicity	$\geq 2$ prolonged clinically significant toxicity	Treatment as appropriate	Hold until recovery to $\leq$ grade 1, and then restart at reduced dose.

\* If no recovery after 14 days of holding drug, patients should be discontinued from the study

\*\* If dose has been previously held for grade 2 rash or diarrhea, and grade 2 symptoms recur, or if the patient finds the symptoms unacceptable, hold dose until recovery to  $\leq$  grade 1 and then reduce the dose.

a Recommended dose: 200 mg p.o. b.i.d. (loading dose), followed by 100 mg p.o. b.i.d. for 7-10 days.

If symptoms of the same degree reoccur after re-initiating the treatment at reduced dose a further dose reduction will be required or patients should be discontinued from the study.

Dosing may be interrupted for a maximum of 14 days if clinically indicated and if the toxicity is not controlled by optimal supportive medication. Patients who require an interruption in dosing of  $> 14$  days will discontinue treatment and be taken off study.

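### Section 6.1.1 orders a hold and a reduced restart for drug-related adverse events of any grade, against Table 2 and Section 7.3; the escalation ban also conflicts with Appendix 4

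*Combined protocol and SAP*

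**What the plan says.** Section 6.1.1 opens permissively: "Reduction/interruption of dosing for adverse events may take place at any time during the study". It then sets a rule for any adverse event that the investigator relates to the drug. No grade is named, and the action is mandatory: "treatment will be interrupted until AE resolution and then restarted at reduced dose of erlotinib". The next rule is "Once a patient has a dose reduction for toxicity, the dose will not be re-escalated except in the case of erlotinib related rash".

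The section introduces its table with "The following guidelines in Table 2 outlines dose adjustments according to the most common toxic effects". In Table 2:

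- Grade 1 diarrhea and grade 1 rash read "No intervention", with no dose modification.
- Grade 2 diarrhea and rash also have no dose modification, subject to a footnote that begins "If dose has been previously held for grade 2 rash or diarrhea, and grade 2 symptoms recur". The footnote also covers symptoms that the patient finds unacceptable. In those cases the dose is held and then reduced.
- Grade 3 rash is held until it is at most "grade 2, and then restart the dose". The text above the table adds "In the event of a rash, dose can be re-escalated when rash is" grade 2 or lower.
- Grade 4 diarrhea, grade 4 rash and keratitis of grade 3 or higher lead to discontinuation.

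Section 7.3.1 discontinues erlotinib for diagnosed interstitial lung disease. Section 7.3.4 stops it permanently for gastrointestinal perforation.

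On the upper dose limit, Sections 3.1.2 and 6.1 both rule out any escalation and give no exception. Section 7.3.7 sends the reader to Appendix 4. For a patient who needs a potent CYP3A4 inducer such as rifampicin, Appendix 4 advises considering 300 mg and, if that is tolerated, possibly 450 mg. Section 4.4 asks only for caution with inducers.

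**The concern.** One section contains two rules for the same events, and they often give different actions. The mandatory sentence has no grade limit, while Table 2 is graded and is called a guideline for the commonest toxicities. The synopsis and Sections 3.1 and 3.1.2 do not help, because they refer the reader to Section 6.1.1 as a whole, which holds both rules.

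The conflict falls on rash and diarrhea, which Section 6.1.1 itself names as the major side effects. What is at stake is patient management: whether a patient with a mild, expected reaction stays on 150 mg or is interrupted and reduced. For inducers, one part of the protocol forbids a dose that another part tells the investigator to consider.

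**Working it through.** The plan gives no figure to reproduce. The check sets the texts side by side and asks one question of each Table 2 row: does it call for an action other than a hold followed by a reduced restart?

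| Table 2 row | Action in Table 2 | Differs from the 6.1.1 sentence? |
|---|---|---|
| Keratitis, grade 2 | hold, restart reduced | no |
| Keratitis, grade 3 or higher | discontinue | yes |
| Diarrhea, grade 1 | no change | yes |
| Diarrhea, grade 2 | no change unless footnote applies | yes, conditionally |
| Diarrhea, grade 3 | hold, restart reduced | no |
| Diarrhea, grade 4 | discontinue | yes |
| Rash, grade 1 | no change | yes |
| Rash, grade 2 | no change unless footnote applies | yes, conditionally |
| Rash, grade 3 | hold, restart, dose level not stated | not counted |
| Rash, grade 4 | discontinue | yes |
| Other, grade 2 or higher, prolonged and clinically significant | hold, restart reduced | no |

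**Count.** Rows: 2 + 4 + 4 + 1 = 11. Unconditional differences: 2 (no change) + 3 (discontinue) = 5, and 5/11 = 45%. Conditional differences: 2. Total: 7/11 = 64%. How far a toxicity must recover before restart is not used in the count.

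**Section 7.3.** Diagnosed interstitial lung disease and gastrointestinal perforation are further conflicts, with discontinuation against restart. Section 6.1.1 lists perforation among the known side effects just before the restart sentence. Section 7.3.3 interrupts for liver changes only when they are severe, where the 6.1.1 sentence would interrupt for any related change.

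**Size for one patient.** For a first grade 1 diarrhea, Table 2 keeps 150 mg. The 6.1.1 sentence gives a hold and then the first reduction in Table 1, 100 mg: (100 − 150)/150 = −33%. Re-escalation is barred except for rash, so this cut would last for the rest of treatment. After a grade 1 rash the same cut could later be reversed.

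**Grade 3 rash.** The three other rows that call for a hold say that the restart is at a reduced dose, and this one does not. After a first grade 3 rash the restart dose can be read as 150 mg (Table 2 alone) or 100 mg (the 6.1.1 sentence). The re-escalation condition, rash of grade 2 or lower, is already met at the moment of restart, so it does not settle the matter.

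**Events outside Table 2.** The other-toxicity row starts at grade 2 and requires a prolonged, clinically significant event. For grade 1 dry skin, fatigue or nausea, the only express dose instruction is therefore the ungraded sentence.

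**Escalation.** Against the 150 mg maximum in Sections 3.1.2 and 6.1, the Appendix 4 doses are 300/150 = 2 times and 450/150 = 3 times. The rash exception only restores a dose that was reduced earlier, so it does not resolve this conflict.

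**The case against.** The best reply is that specific text governs general text. Section 6.1.1 opens with permissive wording, says that toxicities are graded, and introduces Table 2 as the guide to dose adjustment. Below the table it limits interruption to toxicity that supportive medication does not control. An investigator who reads the whole section would probably follow Table 2. That carries weight, but no text states it, and it cannot help where Table 2 has no row, as with grade 1 events other than rash or diarrhea.

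A reader might infer that the protocol would have erlotinib restarted after a perforation, a grade 4 rash or grade 4 diarrhea. The documents do not support that as a realistic outcome. Section 6.1 continues treatment only until progression, death or unacceptable toxicity, and the synopsis and Sections 3.1 and 3.1.2 agree. Table 2 stops the drug at grade 4, and Section 7.3.4 makes the stop after perforation permanent. A restart would require the investigator to overlook all of these.

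The row count can also be over-read. Two of the 7 rows depend on the footnote, and the count measures text, not patients.

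On inducers, Appendix 4 is headed as information, puts alternative drugs first and uses advisory wording. Active infection is an exclusion, which makes rifampicin at entry less likely. The conflict is therefore contingent. It remains possible during the study, because inducers are not prohibited and Section 7.3.7 points investigators to that advice.

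**Conclusion.** The point holds as an inconsistency in dosing instructions that should be corrected. Taken as written, the 6.1.1 sentence contradicts Table 2 in 5 of 11 rows outright and in 2 more unless the footnote applies, and it contradicts Sections 7.3.1 and 7.3.4. No order of precedence is given. The main practical hazard is unnecessary interruption and reduction for low-grade events, lasting for those other than rash. For severe events the other safeguards make a wrong restart unlikely. The conflict between the escalation ban and Appendix 4 is separate and stands by itself.

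The conclusion rests on reading the sentence literally. The documents do not say how many of the 30 planned treated patients would meet either conflict, so no patient-level frequency is claimed. A reader might also infer damage to the PFS result, but nothing in the documents supports that: sample size, endpoint and analysis do not depend on these sentences.

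**What to change.** 1. Replace the 6.1.1 sentence with:

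   > Drug-related AEs are managed by toxicity and grade as in Table 2; Section 7.3 governs the events it names and takes precedence. Related AEs below the Table 2 thresholds need no dose change. Where Table 2 calls for a hold and reduced restart, erlotinib is restarted at the next lower level of Table 1 once the recovery stated in Table 2 is reached.

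   Diarrhea and keratitis appear in both texts, and Sections 7.3.2 and 7.3.6 are looser than the stops in Table 2. Add that the Table 2 discontinuations still apply there. The sponsor should also say whether the sentence above Table 2 on more than one toxic effect is meant to cover two grade 1 events.

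2. In the grade 3 rash cell, state one restart dose: either the dose held or the next lower level. If the lower level is chosen, give a re-escalation condition that is not already met at restart.

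3. Reconcile Appendix 4 with Sections 3.1.2 and 6.1 in one of two ways. Either state that the 300 and 450 mg advice does not apply in this study and say what happens to a patient who cannot avoid a potent inducer, or write the increase into 3.1.2 and 6.1 as an explicit exception. The choice is clinical, since Appendix 4 reports a 69% fall in median erlotinib AUC with rifampicin.

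The cost is a short protocol amendment plus that clinical decision. Visits, sample size, endpoint and analysis do not change.

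### Section 6.1.1 tells sites to restart erlotinib at a reduced dose after any drug-related adverse event, against the stop orders in Section 7.3 for gastrointestinal perforation and diagnosed ILD

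*Combined protocol and SAP*

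**What the plan says.** Section 6.1.1 opens by allowing dose reduction or interruption for adverse events at any time. It lists known side effects, including "anorexia, abdominal pain, gastrointestinal perforation, dry mouth, dry eye, and headache". It then gives a general rule for any event the investigator considers drug-related: "treatment will be interrupted until AE resolution and then restarted at reduced dose of erlotinib". After a reduction for toxicity the dose is not raised again, except for erlotinib-related rash.

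The text under Table 1 introduces the next table: "The following guidelines in Table 2 outlines dose adjustments according to the most common toxic effects". Table 2 then gives actions by toxicity and grade. They range from no change (grade 1 diarrhoea or rash), through hold and restart, to stopping; for keratitis of grade 3 or higher, for example, the entry is "Discontinue treatment and seek ophthalmological advice". A final row for other toxicity, described as "prolonged clinically significant toxicity" of grade 2 or higher, ends in a restart at a reduced dose. Treatment also stops if a hold exceeds 14 days.

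Section 7.3.4 requires permanent discontinuation after gastrointestinal perforation. Section 7.3.1 requires interruption while new, unexplained pulmonary symptoms are evaluated, and discontinuation if ILD is diagnosed.

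**The concern.** The general rule is mandatory and unqualified, and it ends in a restart. For two potentially fatal toxicities, another part of the protocol ends in a stop. Nothing in Section 6.1.1 points to Section 7.3, and no sentence ranks the two. The synopsis and Sections 3.1 and 3.1.2 send the reader to Section 6.1.1 for dose reduction, so a site could consult that section alone and find an instruction to restart.

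Two things are at stake. The first is safety: re-exposure after a perforation or a diagnosed ILD. The second is consistent dosing across the five centres and the 30 patients planned for the treatment phase.

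**Working it through.** No statistical figure is involved. The check sets the instructions side by side and counts the rows of Table 2.

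**Step 1. Events with a stop order in Section 7.3.**

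| Event | General rule, 6.1.1 | Table 2 | Section 7.3 |
|---|---|---|---|
| Gastrointestinal perforation, drug-related | Hold, restart at reduced dose | No row of its own; the other-toxicity row restarts at reduced dose | Stop permanently (7.3.4) |
| Diagnosed ILD, drug-related | Hold, restart at reduced dose | No row of its own; the other-toxicity row restarts at reduced dose | Stop (7.3.1) |

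Either of two readings of Table 2 leaves the conflict in place. If the table covers only common toxicities, as its introduction suggests, these events fall outside it and the general rule applies. If they fall in the other-toxicity row, that row also restarts.

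The 14-day limit does not remove the conflict. It ends treatment only when recovery takes longer than 14 days, so an event that resolves sooner still leads to a restart on a literal reading.

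**Step 2. Rows of Table 2 against the general rule.** The table has 2 (keratitis) + 4 (diarrhoea) + 4 (rash) + 1 (other) = 11 rows.

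| Comparison with hold, then restart at reduced dose | Rows | Count |
|---|---|---|
| Agrees | Keratitis 2, diarrhoea 3, other ≥ 2 | 3 |
| Disagrees: no change | Diarrhoea 1, rash 1 | 2 |
| Disagrees: discontinue | Keratitis ≥ 3, diarrhoea 4, rash 4 | 3 |
| Depends on history or tolerance | Diarrhoea 2, rash 2 | 2 |
| Restart dose not stated | Rash 3 | 1 |

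Check: 3 + 2 + 3 + 2 + 1 = 11. Outright disagreement: 2 + 3 = 5 of 11.

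The two grade 2 rows are not counted. They carry no change at first, but their footnote brings in hold and reduce where "If dose has been previously held for grade 2 rash or diarrhea, and grade 2 symptoms recur", or where the patient finds the symptoms unacceptable. The grade 3 rash row says "and then restart the dose" without giving a level. It is not counted either, because it may reflect the rash exception under Table 1: "In the event of a rash, dose can be re-escalated when rash is" grade 2 or lower.

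**Step 3. Search for a precedence rule.** None is stated in Section 6.1, Section 6.1.1 including its tables and footnotes, or Section 7.3. Section 6.1 ends treatment at unacceptable toxicity, without defining the term or tying it to perforation or ILD. Section 4.5 lets the investigator withdraw a patient for an adverse event but does not require it.

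**The case against.** The best defence is that the sentence should not be read apart from its section. Section 6.1.1 opens permissively, ties reductions to the system with the greatest toxicity, requires grading, and then supplies a graded table. On that reading the sentence is a loose summary and Table 2 is the working rule. Read literally, the sentence would leave the no-change cells for grade 1 events without any use, which can hardly be intended. For Table 2 this defence largely succeeds, and those five rows are a secondary wording point.

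For perforation and ILD it does not succeed, because deferring to Table 2 still ends in a restart. It can be added that a specific instruction normally overrides a general one, that Section 7.3 is clear, and that its interruption step for suspected ILD agrees with Section 6.1.1. A careful investigator would probably stop. But the protocol never states that precedence, and the wording points the other way: the restart rule is in mandatory form, the stop orders in advisory form.

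Several stronger readings are tempting but not supported:

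- **Seven or eight conflicting rows, or a percentage of the table as a measure of size.** The extra rows are conditional or ambiguous, and a share of rows is not a share of patients or events.
- **Widespread dose cuts for mild events.** Read literally, related grade 1 diarrhoea would mean 100 instead of 150 mg/day, (150 − 100)/150 = 33% less. That supposes an investigator who ignores the row ordering no change.
- **Conflict with Sections 7.3.2, 7.3.3 and 7.3.5.** These reserve action for more severe cases, so they differ from the general rule in threshold. They do not impose a stop where it imposes a restart; 7.3.5 leaves interruption or discontinuation open.
- **Conflict between Section 7.3.2 and Table 2 for grade 4 diarrhoea.** Section 7.3.2 gives no grade. Severe diarrhoea may correspond to grade 3, where Table 2 also holds treatment. Overlap with grade 4 is possible but not shown.

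**Conclusion.** The point stands for gastrointestinal perforation and diagnosed ILD: two events for which an unqualified rule orders a restart and Section 7.3 orders a stop, with no stated precedence. This is an unsafe instruction if followed as written, not merely a missing detail. The inconsistency with five of the 11 rows of Table 2 is real but secondary.

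The conclusion assumes that the event is judged drug-related and, for the harm to occur, that it resolves within the 14-day hold limit and that the investigator follows Section 6.1.1 over Section 7.3. The documents give no basis for estimating how often all of this would happen. Section 7.3.1 reports ILD-like events in about 0.6% of erlotinib patients across studies. That figure says nothing about attribution or recovery time in this trial, and Section 7.3.4 gives no rate for perforation. A reader should not infer that patients would in practice be re-exposed at any particular rate.

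This is a matter of patient safety and consistent dosing. No sample size, precision or analysis result changes. It should be fixed.

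**What to change.** Replace the general sentence in Section 6.1.1 with:

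> For AEs related to study drug, erlotinib will be continued, held, reduced or discontinued as specified in Table 2; discontinuation instructions in Section 7.3 (including GI perforation and diagnosed ILD) take precedence and erlotinib must not be restarted after these events.

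Exclude both events from the other-toxicity row of Table 2.

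Replacing the sentence is better than putting an exception in front of it. With an exception alone, the old rule would still hold and reduce the dose for mild related events that Table 2 does not cover, such as grade 1 dry skin or fatigue.

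Separate rows for perforation and ILD, and a stated restart dose for grade 3 rash, would help but are optional.

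The cost is one replaced sentence and one exclusion in a table row. No procedure is added and no analysis changes.

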**Table 1 Dose Level Reductions**

Starting Dose	First reduction	Second reduction
150 mg/day	100 mg/day	50 mg/day

The following guidelines in Table 2 outlines dose adjustments according to the most common toxic effects. In the event of a rash, dose can be re-escalated when rash is  $\leq$  grade 2. Should a patient experience more than one toxic effect, the dose should be reduced.

**Table 2 Guidelines for management of erlotinib-related toxic effects:**

Toxicity	Grade	Guideline for management	Dose modification of erlotinib*
Keratitis	2	Interrupt the treatment. Ophthalmologic assessment.	Hold until recovery, and then restart at reduced dose. Continue regular ophthalmological assessments while

			on treatment.
	$\geq 3$	Discontinue treatment and seek ophthalmological advice	
Diarrhea	1	No intervention	None
	2	Loperamide (4 mg at first onset, followed by 2 mg every 2-4 hours until diarrhea-free for 12 hours)	None**
	3		Hold until recovery to $\leq$ grade 1, and then restart at reduced dose.
	4	Discontinue treatment	
Rash	1	No intervention	None
	2	Any of the following: minocycline a , topical tetracycline or clindamycin, topical silver sulfadiazine, diphenhydramine, oral prednisone (short course)	None**
	3		Hold until recovery to $\leq$ grade 2, and then restart the dose.
	4	Discontinue treatment	
Other toxicity	$\geq 2$ prolonged clinically significant toxicity	Treatment as appropriate	Hold until recovery to $\leq$ grade 1, and then restart at reduced dose.

\* If no recovery after 14 days of holding drug, patients should be discontinued from the study

\*\* If dose has been previously held for grade 2 rash or diarrhea, and grade 2 symptoms recur, or if the patient finds the symptoms unacceptable, hold dose until recovery to  $\leq$  grade 1 and then reduce the dose.

a Recommended dose: 200 mg p.o. b.i.d. (loading dose), followed by 100 mg p.o. b.i.d. for 7-10 days.

If symptoms of the same degree reoccur after re-initiating the treatment at reduced dose a further dose reduction will be required or patients should be discontinued from the study.

Dosing may be interrupted for a maximum of 14 days if clinically indicated and if the toxicity is not controlled by optimal supportive medication. Patients who require an interruption in dosing of  $> 14$  days will discontinue treatment and be taken off study.

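### Section 6.1.1 is inconsistent on the restart dose after grade 3 rash, and its recurrence rule does not cover a restart at full dose

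*Combined protocol and SAP*

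**What the plan says.** Section 6.1.1 gives a general rule. When the investigator judges an adverse event related to study drug, "treatment will be interrupted until AE resolution and then restarted at reduced dose of erlotinib". It then adds that, after a reduction for toxicity, "the dose will not be re-escalated except in the case of erlotinib related rash".

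Table 1 sets the steps: 150, 100 and 50 mg/day. The text between the two tables adds two further rules. The first is "In the event of a rash, dose can be re-escalated when rash is" grade 2 or lower. The second is "Should a patient experience more than one toxic effect, the dose should be reduced".

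Table 2 gives instructions by toxicity and grade. For grade 3 rash, the drug is held until rash is at or below "grade 2, and then restart the dose". For grade 2 keratitis the instruction is "Hold until recovery, and then restart at reduced dose". The grade 3 diarrhea and other-toxicity cells also restart at a reduced dose.

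A footnote to the grade 2 rash and diarrhea cells covers grade 2 symptoms that recur after an earlier grade 2 hold, "or if the patient finds the symptoms unacceptable, hold dose until recovery to" grade 1 or lower, followed by a reduction. Below the table stands the recurrence rule: "If symptoms of the same degree reoccur after re-initiating the treatment at reduced dose a further dose reduction will be required", with discontinuation as the alternative.

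**The concern.** Section 6.1.1 names rash as one of the two major side effects of erlotinib, so a hold for grade 3 rash is a foreseeable event. An investigator who follows the general rule restarts at a reduced dose. One who follows the table cell may restart at the dose the patient was taking, possibly with grade 2 rash still present. Both are acting within the text.

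The recurrence sentence should be the safeguard, but it is tied to a restart at reduced dose. Under the table reading, the patient restarted at the higher dose is the one it does not cover. What is at stake is dosing safety and consistency between sites, not the analysis. Progression-free survival is a Kaplan-Meier summary (section 8.2), and drug exposure is summarized descriptively (section 8.2.2).

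**Working it through.** No sample-size or power figure is involved, so the check is a comparison of the texts.

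**1. The hold-and-restart cells of Table 2**

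| Cell | Hold until | Restart dose named |
|---|---|---|
| Keratitis, grade 2 | recovery | reduced |
| Diarrhea, grade 3 | grade 1 or lower | reduced |
| Rash, grade 3 | grade 2 or lower | none |
| Other toxicity, grade 2 or higher | grade 1 or lower | reduced |

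Four cells hold and restart, and three of them name a reduced dose. The rash cell is also the only one that sets grade 2 as the threshold for restarting.

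**2. The rash cell against the general rule.** They differ on dose (none named, against reduced) and on timing (grade 2 or lower, against resolution of the event). The general rule exempts rash only from the ban on re-escalation, and that exemption applies once a reduction has been made.

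**3. Which text governs?** The general rule cannot be applied literally throughout, because it interrupts treatment for every related event while Table 2 gives no dose change for grade 1 rash and diarrhea, nor for grade 2 apart from the footnote. Sites must sometimes let the table override the text. The section does not say whether they should do so here.

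**4. Which patients?** A patient with more than one toxic effect is reduced under the sentence before Table 2. The conflict is therefore confined to grade 3 rash as the only toxic effect.

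**5. Dose at the moment of restart, from Table 1**

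- From 150 mg/day: 100 or 150 mg/day, and (150 − 100)/150 = 33% lower under the general rule.
- From 100 mg/day: 50 or 100 mg/day, and (100 − 50)/100 = 50% lower.

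**6. How long does the difference last?** The hold ends at grade 2 or lower, and rash re-escalation is permitted at grade 2 or lower. The thresholds coincide. A patient restarted at 100 mg/day could be returned to 150 mg/day at once, so the figures in step 5 describe the restart dose only.

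**7. Recurrence of grade 3 rash**

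| Situation | Recurrence sentence |
|---|---|
| Restarted at reduced dose and still on it | applies: reduce further or discontinue |
| Restarted at full dose (table reading) | does not apply; patient returns to the same cell |
| Restarted at reduced dose, then re-escalated | does not clearly apply; patient is no longer on the reduced dose |

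The second row arises only if the table governs. The third can arise under either reading.

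**The case against.** The strongest objection is that the rash wording may be intended. The protocol is more lenient on rash in several places: it alone may be re-escalated, re-escalation is allowed at grade 2, and its hold ends at grade 2 rather than grade 1. A first grade 2 rash continues without reduction, so 150 mg/day with grade 2 rash is a state the protocol already accepts. The re-escalation exemption does not prove that the grade 3 cell must contain a reduction, because the footnote and the multiple-toxicity rule also produce rash reductions. All of this stands. A reader might infer that the cell is a drafting error that authorises unsafe dosing, and the documents do not support that.

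A reader might also infer that reduced restarts cap the number of restarts while the rash cell allows any number. That contrast assumes no re-escalation, which is the very thing permitted for rash. Other limits exist too: discontinuation at grade 4, the 14-day limit on holds, and investigator withdrawal for adverse events (section 4.5).

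Nor does the footnote need changing. It is attached to the grade 2 row. Once rash has fallen to grade 2, the patient is in that row, and the footnote already requires a hold and a reduction if the symptoms are unacceptable to the patient.

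The defence does not remove the recurrence gap. If a full-dose restart is intended, the recurrence rule should cover it. If it is not intended, the cell should say so.

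**Conclusion.** Section 6.1.1 gives conflicting instructions on the restart dose after grade 3 rash. Under the table reading, it requires no reduction when grade 3 rash returns after a full-dose restart. The text is also unclear for recurrence after re-escalation. This is an inconsistency with a dosing consequence that should be corrected, not a demonstrated dosing error.

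The size is one dose step at restart, for patients whose only toxic effect is grade 3 rash, and it may be short-lived. The treatment phase is planned for 30 patients at 5 centers (sections 3.2 and 3.3). The documents give no rash rate from which to say how many would be affected. No sample size, endpoint or analysis result changes.

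**What to change.** (a) In the recurrence sentence below Table 2, drop the words *at reduced dose* and add re-escalation. A recurrence of the same grade after any restart or re-escalation then requires a dose reduction or discontinuation. The word *further* should go too, since a full-dose restart has involved no earlier reduction.

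(b) Make the grade 3 rash cell restart at a reduced dose, in line with the general rule and the other three cells. In the text before Table 2, state that re-escalation for rash comes only after a period on the reduced dose, and give its length. Without that second part, changing the cell achieves little, because the two thresholds coincide. Table 1 has no level below 50 mg/day, so for a patient already there the cell should point to discontinuation, which the recurrence sentence already offers as the alternative.

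The cost is rewording one cell and two sentences, with the ethics committee approval that section 12 requires. A few patients would receive a somewhat lower dose, with re-escalation still available. Visits, data collection and sample size do not change.
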